9.6. Data management

9.6.1. Source documents and source data

The purpose of source documents is to record the existence of the participant and substantiate the integrity of the trial data collected. The Investigator must maintain the trial source documents accurate,

complete, legible and up to date.

Examples of source documents are: participant screening, laboratory measure reports, enrolment log, participant's diary cards, hospital records, informed consent forms, investigational dispensing and reconciliation forms, participant's file and records kept at the pharmacy or at the laboratories, mail, certified letters.

Source data are the data contained in source documents (originals or certified copies). The investigator is responsible for the accuracy and completeness of the data reported in source documents. Data reported in the CRFs that are derived from source documents should be consistent with source documents and any discrepancies should be explained.

All CRFs must be signed by the Investigator. Incorrect data must be crossed-out with a single line, then initialed and dated. Correction fluid or similar corrective methods that mask the original data will not be used. These rules also apply to the completion of SAE Reporting Forms, Data Correction Forms, and ICFs.

9.6.2. Clinical data management

The investigators should fill in all case report forms (CRF). CRF is used to record data in clinical trials, is an important part of clinical trials and research reports, filling shall be clear and intact, and also should be completed with Chinese language and black pen. Only authorized investigators could correct the errors in the CRFs, The original record can't be obliterated or overwrite. Investigator should draw a horizontal line across the original data which should be corrected, and specify the corrected data in the space next to them, and noted the signature and date.

According to the project requirements, the data collection, biological sample collection and examination should be done in the visit window, the original documents and records shall be complete and the results of the examination also should be timely entered into case report form (CRF).

Auditors should conduct regular and irregular audits of data records until CRF are completed, auditors should carefully verify CRF number of the participants, the number of pages in each CRF and necessary signatures of researchers. The main contents of audits should be focused on signed informed consent, volunteer screening into the group, vaccination, management of the investigational vaccine, safety observation and immunogenicity of specimen collection and preservation, Consistency between research

data and the original data is the emphasis of audits. Manual verification results shall be recorded. Transfer of CRF research data should be documented. For each batch of data, double entry, quality control and triggers to computerized logic and/or consistency checks will be systematically applied in order to detect errors or omissions. Queries will be generated and submitted through Data Clarification Forms to the Investigator for resolution.

9.6.3. Database creation and data entry

— Database creation

The person, who is responsible for data management, establish the database structure and inspection procedures to ensure that the database can be correctly converted to SAS file format, and the database structure can also be modified and confirmed by tentative data entry.

— Verification of CRF

Before CRF entry, data management staff will carry out the CRF verification again, mainly to see if there are obvious errors and omissions.

— Data entry

Data entry staff will start data entry after several training, double entry will be accepted.

— Comparison and check of data

The consistency check of the database that be independently completed by two persons will be executed. Inconsistent values and information should be reported. After that, the raw data will be checked one by one and the mistake will be corrected until database is left in a consistent state. The computer program that has been prepared and confirmed will be applied to do logical consistency check. Before modifying the database, Query table should be shown and confirmed by researchers until there is no question. A certain proportion of CRF will be randomly selected to finish quality control, and to compare with the data in the database, to ensure that the data in the database and the CRF content are consistent.

9.6.4. The database lock

Blind review of the database is required before Statistical analysis. The aim of blind review is to determine the population that will be analyzed according the evaluation criteria, including full analysis

set (FAS) under the Principle of ITT (intention to treat analysis) , per-protocol set (PPS) and safety analyzes data set, confirmation of the deviation from the project and other influences on database. Database will be locked after blind review be confirmed.

9.7. Statistics plan and statistical analysis

9.7.1. Sample size calculation

According to the results of Phase I clinical trial in Jiangsu, we assume that the positive rate of low-dose and high-dose vaccine groups was 85% and 95% respectively and placebo no more than 5%. The allocation ratio will be set as (high-dose: low-dose: placebo)=2:1:1. In order to assure at least 80% of certainty to identify the difference when the lower dose is compared with the higher dose at α value is 0.05, at least 197 participants in high-dose vaccine group and 99 participants in low-dose vaccine group are needed. Around 15% visit loss rate is assumed so we set the sample size as 250 people in high-dose vaccine group, 125 people in low-dose and placebo group, respectively. The total sample size is 500 people.

9.7.2. Interim analysis

After the last participant complete the Visit 3 (28 days after vaccination), the data of the clinical trials from Visit 1 to Visit 3, will be entered into the database for blind review. Then database (Visit 1 to 3) is locked, interim analysis will be done by the independent statistical party. Statistical party must not divulge blinded code. The clinical trial sites still remain in blinded.

9.7.3. The final analysis

After the last participant complete the Visit 4 (168 days after vaccination), database entry is completed, blind review is finished and database is locked, the final analysis will be done by the independent statistical party.

9.7.4. Analyzed data sets definition

9.7.4.1. Data set for safety evaluation

All randomized participants who received vaccination should be included in the safety evaluation. Thus, the safety analysis will be performed on the basis of (Intention-To-Treat) ITT cohort. Events will be reported on per-individual basis, i.e. counting individuals rather than events. This means that even if a participant suffered a same event repeatedly during the follow-up, the event will be counted only once, except for SAEs. Repeated same adverse events in participant will be summarized according to the following rule: if a participant suffered the same adverse event more than once, the event will be assigned the worst severity, the closest relationship to the vaccination and the earliest starting date. In the listings, however, all occurrences of the adverse events will be shown.

9.7.4.2. Data set for immunogenicity evaluation

Full analysis set (FAS) for immunogenicity analysis: FAS is based on ITT (intention to treat analysis) principle to determine the participants. All of the participants that meet the inclusion / exclusion criteria, randomization, receiving vaccination, and have at least one blood testing result after vaccination ,were included in the FAS set for immunogenicity.

Per-protocol set (PPS): It is a subset of FAS. In this set, all participants that meet the inclusion / exclusion criteria and complete the vaccine inoculation within visit window according to the protocol, and complete the blood collection on day 0, 14 and 28, with no significant deviation or violation of protocol.

In this study, the FAS are the primary analysis set for immunogenicity evaluation, but the PPS will also be analyzed at the same time. Any difference of analysis results existed between PPS and FAS, will be discussed in the report.

9.7.5. Statistical methods

9.7.5.1. Safety analysis methods

Safety analysis of this experiment is mainly descriptive analysis of incidence rate of adverse reaction

or adverse events. A chi-square test can be used to compare the proportion of participants with adverse reactions in different groups, Fisher's exact test will be used when it is necessary.

9.7.5.2. Immunogenicity analysis methods

Analysis of immunogenicity indicators on antibody levels need to do logarithmic transformation, the results of analysis should be shown in GMT, standard deviation, median, minimum and maximum values and 95% confidence intervals. ANOVA will be used to compare the GMTs among different groups, and then SNK methods will be used for further pairwise multi-comparison. Chi-square test can be used to compare categorical indicators between groups such as positive conversion rate of immune response, if it is necessary, Fisher's exact test will be used. Statistical analysis method of repeated measures data can be used to analyze experimental data at different time points in this study.

SAS software was used for all analyses, test statistics and the corresponding p values are given. All statistical tests were two-sided and significance was set at $P \leq 0.05$ (more detailed information, please read the reference the statistical analysis plan (SAP)).

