7.2.1.2. Immunogenicity

- ELISA antigen-specific assays for antibody to GP responses on day 0, 14, 28 and 168 (month 6).

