9.5. Laboratory assay and immunogenicity assessments

9.5.1. Zaire Ebola virus GP-specific antibody responses

9.5.1.1. Time point

Serum antibody titers against the Zaire Ebola virus GP will be determined at day 0 (immediately before vaccination), day 14, day 28, and day 168 (month 6).

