9.5.2. Neutralizing antibody titers response to Ad5

9.5.2.1. Time point

Neutralizing antibody titers response to human Ad5 will be detected at day 0, day 14, day 28 and day 168 (month 6).

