9.5.2.3. Evaluation

The neutralizing antibody titers against human Ad5 pre-vaccination and the post-vaccination will be compared to reveal the difference. The relationship between the pre-existing antibody titers against Ad5 and the specific immune response against Zaire Ebola virus (including both humoral and cellular responses) will be explored.

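### The GMT comparison is fixed as an unadjusted ANOVA although day-0 Ad5 and anti-GP titres are measured in everyone; this is valid but may forgo precision on high versus low dose

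*Protocol*

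**What the plan says.** The primary immunogenicity endpoint is the anti-GP ELISA response on days 0, 14, 28 and 168 (section 7.2.1.2). Section 9.7.5.2 puts titres on the log scale and then fixes the between-group method: "ANOVA will be used to compare the GMTs among different groups", followed by SNK tests between pairs of arms. No covariate is named. The same section adds that "Statistical analysis method of repeated measures data can be used to analyze experimental data at different time points in this study", without giving a model or a baseline term, and refers to the SAP for further detail.

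Both candidate covariates are already in the schedule. Section 9.5.1.1 states: "Serum antibody titers against the Zaire Ebola virus GP will be determined at day 0 (immediately before vaccination), day 14, day 28". Section 9.5.2.1 schedules the Ad5 neutralising titre at the same visits, and Table 7-3-2 shows both assays at V1 for all participants.

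The only stated use of the day-0 Ad5 titre against the Ebola response is in section 9.5.2.3, where "The relationship between the pre-existing antibody titers against Ad5 and the specific immune response against Zaire Ebola virus" is to be explored.

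**The concern.** The protocol considers it possible that pre-existing immunity to the vector is linked to the response to the vaccine, and it measures that immunity in everyone before vaccination. It then leaves the measurement out of the comparison on which dose selection partly rests. If the link exists, the variance that it explains stays in the ANOVA error term and the interval for the dose contrast is wider than it need be.

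This matters most for high versus low dose. The trial is meant to pick a dose for phase III (sections 1 and 6). The only earlier data on these two doses, from African participants in China (section 4.2), gave similar titres, so the difference to be judged may be modest. The sample size was set on positive rates (section 9.7.1), so the design does not separately secure precision on the GMT scale.

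**Working it through.** **The plan's own figure.** Section 9.7.1 assumes positive rates of 85% (low dose) and 95% (high dose), two-sided 0.05, 80% power and 2:1 allocation. With pooled rate (0.85 + 2 × 0.95)/3 = 0.9167, the low-dose number is

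[1.960 × √(1.5 × 0.9167 × 0.0833) + 0.8416 × √(0.85 × 0.15 + 0.95 × 0.05/2)]² / 0.10² = (0.6635 + 0.3273)² / 0.01 = 98.2.

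That is 99 low dose and 2 × 98.2 = 196.3, so 197 high dose, as stated. The protocol gives no matching figure for GMTs.

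**Inputs for the GMT contrast.**
- Evaluable numbers after 15% loss (section 9.7.1): 250 × 0.85 = 212 high dose and 125 × 0.85 = 106 low dose.
- Spread, from the Jiangsu phase I day-28 intervals (section 4.2), with n = 40 per arm (high dose by subtraction from 120) and t on 39 df = 2.023:
  - low dose: log10(1098.5/424.3)/2 × √40/2.023 = 0.65
  - high dose: log10(1757.2/970.1)/2 × √40/2.023 = 0.40
  - pooled at 2:1: √[(2 × 0.403² + 0.646²)/3] = 0.50 (0.498 unrounded)
- R², the share of within-arm log-titre variance explained by the day-0 titres: **assumed**. The values 0.04, 0.09 and 0.25 correspond to correlations of 0.2, 0.3 and 0.5.

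**Formulas.** SE = 0.498 × √(1/212 + 1/106) × √(1 − R²) = 0.0592 × √(1 − R²) on the log10 scale. Detectable ratio = 10^(2.80 × SE). CI half-width as a fold factor = 10^(1.96 × SE). Equivalent extra participants = 1/(1 − R²) − 1. Power = Φ(log10(ratio)/SE − 1.96).

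| Assumed R² | SE factor | Equivalent extra participants | CI half-width (fold) | Ratio detectable, 80% power | Power if true ratio is 1.4 |
|---|---|---|---|---|---|
| 0 (ANOVA) | 1 | – | 1.306 | 1.465 | 69.5% |
| 0.04 | 0.980 | 4% | 1.299 | 1.454 | 71.2% |
| 0.09 | 0.954 | 10% | 1.290 | 1.439 | 73.5% |
| 0.25 | 0.866 | 33% | 1.260 | 1.392 | 81.4% |

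**Sensitivity to the SD.** For log10 SD from 0.40 to 0.65, the detectable ratio runs from 1.36 to 1.64 unadjusted, and from 1.31 to 1.54 at R² = 0.25.

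**Against the earlier trials.** The African phase I ratio is 1918.7/1684.7 = 1.14, with the lower dose the higher. Power at that ratio is 16% unadjusted and 20% at R² = 0.25. The Jiangsu ratio is 1305.7/682.7 = 1.91, for 1.6×10^11 against 4×10^10 vp, and power there exceeds 95% at every SD tried. Adjustment can therefore change the result only for differences in between, such as 1.4.

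**The case against.** The best defence is that nothing here is wrong. Unadjusted ANOVA on log titres is valid under randomisation, and chance imbalance at baseline is already covered by its error rate and interval. Covariates are often left to the SAP, which section 9.7.5.2 cites and which is not at hand. The validity argument stands in full. The SAP argument stands only in part: the sentence fixes a method rather than leaving one open, so replacing it with a more precise method is a fair suggestion. The optional repeated-measures analysis could bring in day 0, but nothing commits it to do so.

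Several stronger readings are tempting and are not supported:

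- **That the protocol treats Ad5 immunity as a determinant of response.** Section 9.5.2.3 says only that the relationship will be explored. For the same reason, the protocol as a whole does not ignore the measurement; only the stated GMT comparison omits it.
- **That the placebo comparisons also suffer.** Section 9.7.1 assumes 85% to 95% positive on vaccine against at most 5% on placebo, so precision is not limiting there. Nor is there an evident reason for day-0 Ad5 titre to predict anti-GP titre in people given no vector.
- **That both baseline titres would contribute equally.** Section 8.3 excludes Ebola infection and prior Ebola vaccination, so day-0 anti-GP titres should lie near the assay floor and explain little.
- **That the detectable ratio falls from 1.56 to 1.47.** This results from applying the phase I arm-specific SDs (natural log about 1.49 and 0.93, SE 0.158) and a correlation of 0.5. It puts the spread of a 4×10^10 vp dose, which is not an arm here, on the low-dose arm, and it uses the favourable correlation. At 0.3 the fall is only to exp(2.8 × 0.158 × √0.91) = 1.53.

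**Conclusion.** The point holds as an available improvement, not as an error. The named GMT comparison is unadjusted, both day-0 titres exist for everyone at no extra cost, and adjustment could sharpen the high-versus-low contrast. The likely benefit runs from negligible (SE about 2% smaller at R² = 0.04) to useful (about 13% smaller at R² = 0.25, which takes power at a true ratio of 1.4 from 69.5% to 81.4%).

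This rests on three assumptions: an R² for which the protocol offers no evidence; a pooled log10 SD of 0.50 that borrows in part from a phase I dose not used here; and the planned 15% loss. A reader might infer that adjustment would settle the dose question. It would not do so if the true ratio is near 1.14, where power stays at or below about 20% across the R² values tabulated.

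**What to change.** In section 9.7.5.2, and to match in the SAP, name ANCOVA on log titre as the analysis of high versus low dose, with arm, log day-0 Ad5 neutralising titre and log day-0 anti-GP titre as prespecified terms. If placebo is kept in the same model, let its Ad5 slope differ from that of the vaccine arms. Report the adjusted GMT ratio with its 95% CI, and keep the unadjusted GMTs as description.

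The cost is a few lines of text and two degrees of freedom. No sample, visit or assay is added. The wording should be in place before the day-28 database lock, because section 9.2.3 has the data unblinded after that visit and a covariate chosen later would look data-driven.

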4.2. Background of Vaccine

The EBOV envelope glycoprotein (EBOV-GP) forms spikes on the surface of mature virion, and has been shown to be an effective target for vaccine design. GP protein was used as a protective antigen in the Ebola virus vaccine in clinical study process.

Data of our Phase I study on Ad5-EBOV in healthy Chinese people was published on Lancet. 120 participants were enrolled and randomly assigned to receive placebo (n=40), low-dose vaccine (n=40), or high-dose vaccine. Participants were followed up for 28 days. Overall, 82 (68%) participants reported at least one solicited adverse reaction within 7 days of vaccination (n=19 in the placebo group vs n=27 in the low-dose group vs n=36 in the high-dose group; p=0.0002). The most common reaction was mild pain at the injection site, which was reported in eight (20%) participants in the placebo group, 14 (35%) participants in the low-dose group, and 29 (73%) participants in the high-dose vaccine group

($p < 0.0001$). We recorded no statistical differences in other adverse reactions and laboratory tests across groups. Glycoprotein-specific antibody titers were significantly increased in participants in the low-dose and high-dose vaccine groups at both day 14 (geometric mean titer 421.4 [95% CI 249.7- 711.3] and 820.5 [598.9-1124.0], respectively; $p < 0.0001$) and day 28 (682.7 [424.3-1098.5] and 1305.7 [970.1-1757.2], respectively; $p < 0.0001$). T-cell responses peaked at day 14 at a median of 465.0 spot-forming cells (IQR 180.0-1202.5) in participants in the low-dose group and 765.0 cells (400.0-1460.0) in those in the high-dose group. 21 (18%) participants had mild fever ($n=9$ in the placebo group, $n=6$ in the low-dose group, and $n=6$ in the high-dose group). No serious adverse events were recorded. It was proved the vaccine is safe and has high immunogenicity. GP specific humoral immune was stimulated on day 14 after primary vaccination in high dose group.

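### The planned ANOVA with SNK pools one variance over all three arms, which would make the high versus low dose GMT test liberal if placebo titres vary little, and more so if the low-dose arm is the more variable

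*Protocol*

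**What the plan says.** Section 9.7.5.2 of the protocol puts titres on a log scale ("Analysis of immunogenicity indicators on antibody levels need to do logarithmic transformation") and then fixes the test: "ANOVA will be used to compare the GMTs among different groups, and then SNK methods will be used for further pairwise multi-comparison". "All statistical tests were two-sided and significance was set at" P ≤ 0.05. The section names no variance check and no unequal-variance alternative. It allows repeated-measures methods without saying how the variance is modelled, and it refers to the SAP for more detail.

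Three other places matter:
- Section 9.7.1 fixes the allocation: "The allocation ratio will be set as (high-dose: low-dose: placebo)=2:1:1", that is 250, 125 and 125 participants. It assumes "positive rate of low-dose and high-dose vaccine groups was 85% and 95% respectively and placebo no more than 5" per cent.
- Section 4.2 gives the Jiangsu phase I day-28 GMTs with 95% intervals, low then high dose: "682.7 [424.3-1098.5] and 1305.7 [970.1-1757.2], respectively". That low dose was 4×10^10 vp (section 5.4.1). The low dose here is 8×10^10 vp.
- The phase I trial in African participants (section 5.4.2) used both doses of this trial. Its day-28 GMTs were 1918.7 (8×10^10 vp) and 1684.7 (1.6×10^11 vp), with no measure of spread.

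**The concern.** A test with a pooled error holds its level only if the arms have about the same variance. Two features of this trial put that in doubt for the dose comparison.

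First, an arm in which almost nobody is positive may show little spread in log titre. Its 125 values would then pull down the residual variance against which the two doses are compared. Secondly, the phase I intervals imply a larger SD in the low-dose group. Here the low-dose arm has half as many participants as the high-dose arm, and when the smaller arm is the noisier one, pooling understates the standard error.

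SNK does not guard against this. With placebo far below both doses, the three-group step is expected to reject, and the dose contrast is then tested at the two-group critical value. That is an unadjusted t test on the pooled error.

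Choosing a dose for phase III is a stated objective, and GP antibody is the primary immunogenicity measure. Because the African phase I trial found similar GMTs at these two doses, equal means are a realistic possibility, so the false-positive rate matters.

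**Working it through.** **The plan's own figure.** The protocol gives no error rate for the GMT test beyond P ≤ 0.05. Its sample-size figure concerns the positive rate. For 85% versus 95% with 2:1 allocation, two-sided 0.05 and 80% power, the usual pooled formula without continuity correction gives 99 low and 198 high (stated: 99 and 197). Power at 99/197 is 80.2%, so the figure reproduces.

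**Phase I SDs.** With 40 per group (120 in total, 40 placebo, 40 low) and t(0.975, 39) = 2.023, SD = log10(upper/lower) / (2 × 2.023) × √40.
- Day 28 low: log10(1098.5/424.3) = 0.4131, SD 0.646.
- Day 28 high: log10(1757.2/970.1) = 0.2580, SD 0.403.
- Day 14, from the intervals in the same section: low 0.711, high 0.427.

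The day-28 SD ratio is 1.60 (95% CI 1.16 to 2.20, F test p = 0.004).

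**Assumptions.** Placebo log10 SD of 0 to 0.3. Dose SDs either equal at 0.5 or as in phase I. The documents fix neither.

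**Formulas.** Let H, L and P be the high, low and placebo arms.
- MSE = (249 s_H² + 124 s_L² + 124 s_P²) / 497
- SE used by the test = √[MSE × (1/250 + 1/125)]
- True SE = √(s_H²/250 + s_L²/125)
- Actual size = 2Φ(−1.965 × SE used / true SE)

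If SNK uses the harmonic-mean n, that is 3/(1/250 + 1/125 + 1/125) = 150, and SE used = √(MSE × 2/150).

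**Worked cases, placebo SD 0.**
- Equal dose SDs of 0.5: MSE 0.1876, SE used 0.0475, true SE 0.0548. 1.965 × 0.0475/0.0548 = 1.70, size 8.9%.
- Phase I SDs: MSE 0.1855, SE used 0.0472, true SE 0.0632. 1.965 × 0.0472/0.0632 = 1.47, size 14.2%.

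Actual size (%) of the nominal 5% high versus low test:

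| Dose SDs (high/low) and n used | P SD 0 | 0.1 | 0.2 | 0.3 | 0.5 |
|---|---|---|---|---|---|
| 0.5/0.5, actual n | 8.9 | 8.7 | 8.1 | 7.2 | 4.9 |
| 0.5/0.5, harmonic n | 7.3 | 7.1 | 6.6 | 5.8 | 3.8 |
| 0.403/0.646, actual n | 14.2 | 13.9 | 13.2 | 12.0 | 9.0 |
| 0.403/0.646, harmonic n | 12.2 | 11.9 | 11.2 | 10.1 | 7.4 |
| 0.646/0.403, actual n | 4.8 | 4.7 | 4.4 | 3.9 | 2.7 |

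For a low-dose SD between equal and phase I (1.3 times a high-dose SD of 0.403), placebo SD 0 to 0.3 gives 11.8% to 9.4%. Results at 212/106/106, after 15% loss, agree within 0.1 point.

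Simulation of the full SNK procedure (100,000 runs per scenario) agrees with the formula within 0.3 point. A Welch test on the two dose arms held 4.9-5.1% throughout. Dropping placebo but keeping a common variance for the two doses still gives 9.0% with the day-28 SDs, so removing placebo is not enough by itself.

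**The case against.** The strongest objection is that the inputs that drive the rates are not in the protocol. It gives no placebo titre, placebo SD or assay floor. A low positive rate does not show how much titres vary below the cut-off. The SD of 0.646 belongs to 4×10^10 vp in Chinese adults, a dose not given here. All of this stands, so the rates must be read as conditional.

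A reader might infer more than the documents support:
- **That the test does run at 7-14%.** It would do so only under the stated SDs. With a more variable high-dose arm (last row of the table), or with all SDs equal, there is no inflation. With harmonic-mean SNK, dose SDs of 0.5 and placebo SD 0.4, the size is 4.8%.
- **That the higher dose is favoured.** The tests are two-sided, and under equal means false positives fall either way. In the African phase I trial the lower dose had the numerically higher GMT.
- **That the powered dose comparison is undermined.** The sample size was set "In order to assure at least 80% of certainty to identify the difference when the lower dose is compared with the higher dose" on positive rates, for which section 9.7.5.2 names chi-square or Fisher's test. Pooled variance plays no part in that. Nor does the protocol say that the GMT test alone decides the dose.

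Vaccine versus placebo, the contrast named in section 9.5.1.3, should be separated so widely that the choice of error term hardly matters.

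It can also be said that variance handling belongs in the SAP, which was not available for this check. But the protocol does not leave the test open: it names a pooled-variance procedure. If the SAP already uses separate variances, the two texts need aligning.

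**Conclusion.** The point holds in conditional form. The protocol names a procedure whose error rate for high versus low dose depends on equal variances, and its own phase I intervals give reason to doubt that assumption.

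With placebo log10 SD of 0 to 0.3, a nominal 5% test would run at about 7-9% if the dose SDs are equal at 0.5, and at about 12-14% if the phase I SDs carry over. With harmonic-mean SNK the ranges are about 6-7% and 10-12%. The lower range rests only on an assumed small placebo spread. The upper range also assumes that the SD seen at 4×10^10 vp applies at 8×10^10 vp.

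The inflation disappears if the high-dose arm is sufficiently more variable than the low-dose arm, or if the dose SDs are equal and the placebo SD is about as large. The change is worth making because the risk is plausible and the remedy costs almost nothing.

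**What to change.** In section 9.7.5.2, replace ANOVA plus SNK for the dose comparison with an analysis of log10 titre that gives each arm its own variance: a Welch t-test of the two vaccine arms, or a linear or repeated-measures model with arm-specific variances. Report the high:low GMT ratio with its 95% CI. Bring the SAP into line if it follows the protocol's wording.

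The cost is one sentence and a slightly wider interval. With dose SDs of 0.5, the separate-variance interval for the ratio is the estimate multiplied and divided by about 10^(1.97 × 0.0548) = 1.28. The pooled interval with placebo SD 0 would use 10^(1.965 × 0.0475) = 1.24. If the variances prove equal in all arms, almost no precision is lost. No change to sample size or data collection is needed.
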